TITLE: **3D ROTATIONAL CT ANGIOGRAM WITH EMBOLIZATION
GUIDANCE AND CBCT IN PROSTATE ARTERY
EMBOLIZATION**

Sponsor: **[name]**

**University of Miami
Interventional Radiology
[name]
[name]
[name]**

National Clinical Trial Identifier: **NCT03164629**

VERSION: **B**

Date of Protocol: **February 20, 2018**

1) **Protocol Title**

3D Rotational CT angiogram with Embolization guidance and CBCT in Prostatic Artery Embolization

2) **Primary Objective**

To ascertain the feasibility of cone-beam CT with Embolization Guidance software (Emboguide) to identify prostatic arteries and assist endovascular navigation, by projecting a 3D road map of prostatic arteries on live fluoroscopy, in order to differentiate them from non-target vessels. **The primary outcome measurement will be the time for prostatic artery catheterization.**

- For the cases using Emboguide this will be measured as the time from which the Emboguide is displayed on the live fluoroscopy to the time of prostatic artery catheterization. Emboguide display is in addition to the angiogram roadmap display.
- For the control cases this will be measured as the time from which the angiogram is displayed on the live fluoroscopy to the time of prostatic artery catheterization.

3) **Background**

Direct clinical translation – University of Miami has been performing Prostatic Artery Embolization (PAE) since 2014 and has significant experience with the procedure. Technical challenges are encountered on a routine basis. The combination of 3D rotational CT, Emboguide and cone beam CT has tremendous potential to standardize and optimize a software protocol to aid in identification, catheterization, and embolization during the technically challenging PAE procedure. The data from this feasibility study might be used for a subsequent grant proposal (individually or in conjunction with other proposals) to improve the safety and efficacy of PAE.

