The proposed study is a proof of concept investigation to assess a new clinical application. Current technical challenges to the widespread adoption of PAE include identification and catheterization of arteries appropriate for embolization. Prostate arteries are frequently tortuous, with duplication or replacement and varying sites of origin, and due to the nature of the patient population, atherosclerosis further complicates identification and navigation. An imaging system that could assist with identification and catheterization has the potential to improve patient outcomes by facilitating more complete embolization, avoidance of non-target vessel occlusions, and reduction of radiation exposure time.

With the current proposal, the software application can be standardized and tailored to optimize safety and efficacy of prostate embolization, which has been shown in clinical trials to be an effective alternative treatment of enlarged prostate or bladder outlet obstruction.

Another advantage of the protocol is it may obviate the need for pre-procedure CT angiogram, further reducing radiation exposure and procedure time.

4) **Inclusion and Exclusion Criteria***

Inclusion criteria:

- 1) Patient is age 50 to 79, inclusive
- 2) Patients undergoing Prostate artery embolization for BPH or urinary retention
- 3) Patient has signed informed consent (able to consent).

Exclusion criteria:

- 1) Patients with biopsy proven prostate cancer
- 2) Patient weight of >300 lbs.

5) **Local Number of Subjects***

Approximately 50 patients will be enrolled at this investigator site no screening failures are anticipated since all 50 patients will receive PAE and cone-beam CT. Currently cone-beam CT is performed routinely for all PAE cases. 25 sequential patients will undergo PAE with 3D angiogram and Emboguide. This will be followed by 25 sequential patients who will undergo PAE with no 3D angiogram nor Emboguide.

6) **Study Timelines***

The study duration will be approximately one year from the start date. The enrollment will take about 8 months and data analysis will take about 3 months.

7) **Study Design/Procedures Involved**

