This is a single center prospective study. The patients eligible for the PAE for benign prostate hyperplasia will be offered the study and informed consent will be obtained. Once patient has been referred to Interventional Radiology (IR) and prior to the clinic visit with the IR physician, the records of the patient will be accessed for screening purposes. Patients will be recruited for participation in the study during routine consultation for the prostate embolization procedure. The main challenge of the PAE procedure remains the identification of the prostatic arteries and their super-selective catheterization. Contrast enhanced cone-beam CT (Dyna-CT) is already performed at our center as part of the PAE clinical protocol to reduce the risk of non-target embolization, especially to the rectal, bladder and penile vasculature. We will initially obtain a 3D rotational selective angiography of the internal iliac artery for study group. This dataset will be called the PLANNING dataset. We will assess if superimposing the pre-catheterization 3D dataset (in which the physician marks the prostate and its arterial feeders), can be used as an Emboguide tool along with overlay from a conventional DSA. This will be transmitted to live fluoroscopy and be used as an aid to catheterization of the prostatic arteries in the study group.

Study Group

The following parameters will be recorded for the study group:

- Time for catheterization as defined above
- Time for planning dataset for each side
- Total dose area product
- Dose for planning dataset for each side
- Dose area product only for fluoroscopy
- Total procedural time: **from access to closure**
- Amount of contrast medium used

Control Group

The following parameters will be recorded for the control group:

- Time for catheterization as defined above
- Total dose area product
- Dose area product only for fluoroscopy
- Total procedural time: **from access to closure.**
- Amount of contrast medium used

The tortuosity of the vessels will be graded in each case and will be categorized into:

- 1- Mild
- 2- Moderate
- 3- Severe

This will be graded visually for every case and will be noted on the case report forms. We will also study the arterial supply to the prostate gland with any anatomic variants including duplicated prostatic arteries or prostate arteries arising from less common branches such as common gluteal-pudendal trunk, obturator artery, and inferior gluteal artery in all patients.

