8) **Data Storage**

All data collected will be stored in a password protected database in a password protected computer of Interventional Radiology to which only the PI and study coordinator or other key research personnel have access.

Address: [name]
[name]
[name]

9) **Data Management***

The statistical analysis for the current study will be conducted as follows. The following variables and parameters will be collected:

- Time for catheterization

- Time for planning dataset for each side (This will be evaluated as the time from completion of the 3D angiogram to beginning of catheterization)
- Total dose area product,
- Dose for planning dataset for each side,
- Dose area product for fluoroscopy only,
- Total procedure time, and
- The amount of contrast media used.

Descriptive statistics (mean, median, range, and standard deviation) will be computed for the treatment group and the control group and values will be compared for the variables of interest.

Additionally, a statistical significance comparison between the study group (with guidance) and the control group (without guidance) will be computed for several parameters. Specifically, the differences in means and/or medians between the following variables and parameters will be analyzed using a T-test or a Mann-Whitney test (depending on normality of the distribution and other assumptions):

- Time for prostate artery catheterization for each group
- Total dose area product (this will include DAP from the planning dataset in the study group)
- Dose area product only for fluoroscopy,
- Total procedure time, and
- The amount of contrast medium used.

10) **Withdraw of Subject**

Patients can withdraw from the study at any time, without penalty or benefit. This study may be discontinued, without the patients consent, at any time by the study doctor, if he/she believes that participation in the study is no longer in their best interest.

11) **Risks to Subjects***

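### The primary catheterization time has no value for a side that is attempted but never catheterized, and no listed item records failure, so the comparison covers successes only

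*Combined protocol and SAP*

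**What the plan says.** Section 2 states that "The primary outcome measurement will be the time for prostatic artery catheterization". In the control group it is "the time from which the angiogram is displayed on the live fluoroscopy to the time of prostatic artery catheterization". In the study group the clock starts when the Emboguide overlay appears and stops at the same event.

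Section 7 lists catheterization time once in each group. Planning time and planning dose, recorded in the study group only, are marked as collected by side. The overlay is to "be used as an aid to catheterization of the prostatic arteries in the study group", so more than one artery per patient is foreseen. Neither list in Section 7 nor the list in Section 9 contains an item for success or failure of catheterization.

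The protocol treats this step as hard. Section 3 says "Technical challenges are encountered on a routine basis" and "Prostate arteries are frequently tortuous, with duplication or replacement and varying sites of origin". Section 7 says "The main challenge of the PAE procedure remains the identification of the prostatic arteries and their super-selective catheterization".

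Section 5 counts patients: "25 sequential patients will undergo PAE with 3D angiogram and Emboguide", followed by 25 controls. Section 9 compares "Time for prostate artery catheterization for each group" by a t-test or a Mann-Whitney test, chosen on normality and other assumptions. No rule is given for an artery that is never reached.

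**The concern.** The event that ends the clock is the success that the guidance is meant to bring about. When an attempt fails there is no stop time, and the natural result is a blank cell that drops out of the analysis. The primary comparison then describes how long catheterization took where it worked.

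That is harmless if failures are rare, or unrelated to how long the artery would have taken. It is not harmless if the difficult arteries are the ones that fail and guidance changes how often that happens. The group with more failures then loses more of its slow sides and looks faster than it was. A real saving in time would be understated, and guidance that only turned failures into late successes could look slower than control.

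A feasibility study of a navigation aid needs its failures counted in any case. No follow-up visits are planned (Section 17), so failures and side times not noted during the procedure may not be recoverable. The case report forms mentioned in Section 7 are not among the documents and may hold more.

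**Working it through.** **Plan's own figures.** Only 25 + 25 = 50 can be checked. The plan gives no alpha, power, effect size, SD or failure rate. Everything numerical below rests on assumed inputs and shows direction and size only.

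**Text.** The stop event in Section 2 is catheterization. The lists in Sections 7 and 9 hold times, doses and contrast volume. No section gives a censoring rule, an imputation, an exclusion rule or a success outcome. A failed side therefore has no value.

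**Case A: guidance shortens times by 25%, and the slowest sides fail.** Assume lognormal side times with CV 0.5, so σ = √ln(1 + 0.5²) = √ln 1.25 = 0.4724. Assume a side fails if its time would exceed a fixed limit, the same in both groups. If a fraction Φ(z) of sides succeeds, the mean time of the successes, as a fraction of the mean of all sides, is Φ(z − σ)/Φ(z). Call this a for control and b for guided. With a true ratio of 0.75, z in the guided group is z in control plus −ln(0.75)/σ = 0.2877/0.4724 = 0.6090. The apparent ratio is 0.75 × b/a.

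Worked for 10% control failures:
- a = Φ(1.2816 − 0.4724)/0.90 = 0.7908/0.90 = 0.8787.
- Guided z = 1.2816 + 0.6090 = 1.8906, so Φ = 0.9707 and 2.9% fail.
- b = Φ(1.8906 − 0.4724)/0.9707 = 0.9219/0.9707 = 0.950.
- Apparent ratio = 0.75 × 0.950/0.8787 = 0.811.

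| Control sides failing | Guided sides failing | a | b | Apparent ratio (true 0.75) |
|---|---|---|---|---|
| 5% | 1.2% | 0.926 | 0.974 | 0.789 |
| 10% | 2.9% | 0.879 | 0.950 | 0.811 |
| 20% | 7.3% | 0.805 | 0.902 | 0.841 |

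(Ratios are from unrounded a and b.)

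Simulating whole patients (two sides, log-scale correlation 0.5, 25 v 25, 20,000 runs, mean of the successful sides per patient) gives 0.784/0.804/0.836, that is, apparent reductions of 22%/20%/16%. With CV 0.8 the ratios are 0.795/0.819/0.853.

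Power at two-sided 5% in the same simulation:
- All times known, t-test: 0.64 to 0.65.
- Failed sides dropped, t-test: 0.62/0.59/0.51.
- Patients with a failed side ranked last, Mann-Whitney: 0.64/0.65/0.63.

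**Case B: guidance only prevents failures.** Times have the same distribution in both groups; 15% of control and 5% of guided sides fail, again the slowest.
- Control: Φ(1.0364 − 0.4724)/0.85 = 0.7136/0.85 = 0.8396.
- Guided: Φ(1.6449 − 0.4724)/0.95 = 0.8795/0.95 = 0.9258.
- Apparent ratio = 0.9258/0.8396 = 1.10, so guidance looks 10% slower.

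A separate simulation of the same failure rates (first side only, log-SD 0.7, Mann-Whitney, 4,000 runs) rejects in 8.5% of trials with failures dropped and in 4.7% with failures ranked last. Ranking last removes the spurious result, but it does not detect a benefit confined to failures. That benefit has to be seen in the failure counts.

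**Case C: failures unrelated to time.** The expected time among successes then equals the expected time among all sides in each group, so the ratio stays at 0.75 whatever the failure rates. Only numbers are lost.

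**Case D: no effect and equal failure rates.** Dropping failures rejects in 4.8% to 5.4% of trials, which is nominal.

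**The case against.** The documents never mention a failed side and give no failure rate. Section 5 expects all 50 patients to receive the procedure. The study is described as feasibility and proof of concept, with descriptive statistics planned first. This stands as a limit on the size of the problem, though receiving the procedure does not guarantee success on every side or artery, and the outcome is still named as primary and significance-tested.

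The direction of bias is conditional. It needs failures to be the slow arteries and failure rates to differ. Case C shows that it disappears otherwise, so a reader should not infer that the plan necessarily understates the benefit.

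Ranking failures last is a convention. It treats a patient with one failed side like a patient with two, and it rules out the t-test that Section 9 otherwise allows. Both points stand and count as costs.

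Two stronger readings are tempting:
- A reader might infer that, because the plan does not name the patient-level value, the effect size is undetermined. But first side, mean and sum all estimate the same 25% reduction, and mean and sum give the same test when every patient has two sides. A clock running from the first side to the last is poorly supported: Section 9 makes planning time a separate by-side item, and such a clock could absorb the second side's planning. The unnamed value is mostly missing detail.
- A reader might infer that sides will be entered as independent observations. The plan counts patients, defines the time by case and lists it beside patient-level items, so one value per patient is implied, and the named tests are valid for that.

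**Conclusion.** The point holds as a conditional weakness of the primary analysis that is cheap to repair and should be repaired. As written, the primary comparison is confined to successful catheterizations, and nothing in the listed data shows how many attempts failed. If the slowest arteries fail, a true 25% reduction would appear as 22%/20%/16% at 5%/10%/20% control failures, with power falling to about 0.51 at the highest rate. Guidance that only cuts failures from 15% to 5% would look about 10% slower. These sizes rest on assumed lognormal times, CV 0.5 and failure at a fixed time, none of which the documents state. With failures rare or unrelated to time, the bias is small or absent.

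The documents do not support a claim that the result will be biased in a known direction, or that the false-positive rate is inflated in general. Naming the patient-level value and the artery that stops the clock is a supporting clarification. Confidence is medium, because the case report forms were not available.

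**What to change.** **Recording (Section 7 and the case report form, if not already there).** In both groups, record for each attempted side: the side, clock start, clock stop, and whether catheterization succeeded.

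**Analysis (Section 9).** State in advance that:
- the patient value is the mean of the attempted sides' times, and a patient with one side attempted contributes that side, with the number of such patients reported by group;
- failures are reported by group, by side and by patient;
- the primary test is a Mann-Whitney test with patients who have a failed side ranked last;
- times of successful sides are reported separately and labelled as such;
- on a side with duplicated arteries, a named artery stops the clock, and times for the others are also recorded.

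**Cost.** Four fields for each side and a few sentences; no more patients. There is slightly more recording during the procedure. The t-test option is given up for the primary outcome, so its result is a comparison of ranks and not a difference in mean minutes. The t-test option stays open for the other outcomes.

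### Total and fluoroscopy DAP are compared between two sequential, non-randomised groups without adjustment for body weight, and no body-size measure is recorded: a cheap improvement on non-primary endpoints.

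*Combined protocol and SAP*

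**What the plan says.** - **Allocation (Section 5).** The Emboguide block comes first: "25 sequential patients will undergo PAE with 3D angiogram and Emboguide". The control block comes second: "This will be followed by 25 sequential patients who will undergo PAE with no 3D angiogram nor Emboguide". Group is therefore set by calendar order, with no randomisation, matching or stratification.
- **Endpoints (Section 9).** Two of the five variables tested between groups are radiation measures: "Total dose area product (this will include DAP from the planning dataset in the study group") and "Dose area product only for fluoroscopy".
- **Method (Section 9).** Differences "will be analyzed using a T-test or a Mann-Whitney test (depending on normality of the distribution and other assumptions"). No covariate or sensitivity analysis is named for any endpoint, and no log transformation is mentioned.
- **Weight (Section 4).** One exclusion criterion is "Patient weight of >300 lbs". Neither the recorded-parameter lists in Section 7 nor the variable list in Section 9 contains weight, BMI or any other measure of body size.
- **Status (Section 2).** DAP is not primary: "The primary outcome measurement will be the time for prostatic artery catheterization".
- **Why DAP is measured (Section 11).** The protocol accepts that the planning dataset adds radiation in the Emboguide group, and suggests that quicker catheterization may offset it.

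**The concern.** A larger patient attenuates more of the beam, and a system with automatic exposure control raises its output in response. DAP should therefore rise with body weight. This is general imaging physics, not something the protocol states. Weight is fixed before the procedure and cannot be altered by Emboguide, so it is a legitimate baseline covariate.

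Leaving it out has two possible consequences:

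- **Lost precision.** Variation in DAP due to body size stays in the error term of a comparison with only 25 patients per group.
- **Exposure to imbalance.** If patients in one block are systematically heavier, the unadjusted comparison attributes the resulting DAP difference to Emboguide. The error could go either way, hiding a real dose increase or producing an apparent saving. With no weight recorded, a reader could not even check.

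At stake is the plan's direct test of whether the added planning dose is offset.

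**Working it through.** The documents give no alpha, power, SD, effect size or sample-size calculation, so there is no planned figure to reproduce. What follows is illustrative.

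**Inputs**

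- n = 25 per group (Section 5).
- Two-sided alpha of 0.05: assumed.
- Correlation r between weight and log DAP within groups: not in the documents, varied from 0.2 to 0.6.
- Differences in units of the within-group SD of log DAP.

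**Step 1: unadjusted comparison.** The standard error is √(2/25) = 0.283 SD. With the noncentral t on 48 df, 80% power is reached at a difference of 0.809 SD, and power at 0.6 SD is 54.7%.

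**Step 2: adjusted for weight.** The residual SD is multiplied by √(1 − r²), and effective sample size by 1/(1 − r²). One degree of freedom is spent, leaving 47.

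| r | √(1 − r²) | 1/(1 − r²) | Detectable at 80% power | Power at 0.6 SD |
|---|---|---|---|---|
| none | 1.000 | 1.00 | 0.81 SD | 55% |
| 0.2 | 0.980 | 1.04 | 0.79 SD | 56% |
| 0.3 | 0.954 | 1.10 | 0.77 SD | 59% |
| 0.4 | 0.917 | 1.19 | 0.74 SD | 62% |
| 0.5 | 0.866 | 1.33 | 0.70 SD | 67% |
| 0.6 | 0.800 | 1.56 | 0.65 SD | 74% |

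The gain is slight at r = 0.2 to 0.3 and material from about 0.5 upwards.

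These figures assume that the groups are balanced on weight. If they differ by D SD, the adjusted standard error is multiplied by √(1 + D² × 12.5/48). For D = 0.5 this is √(1 + 0.25 × 12.5/48) = √1.065 = 1.032. At r = 0.2 the net factor is then 0.980 × 1.032 = 1.011, so the precision gain is gone. At r = 0.6 it is 0.800 × 1.032 = 0.826.

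**Step 3: chance imbalance in weight.** The standardised weight difference between two groups of 25 has a standard error of √(2/25) = 0.283 SD (95% range ± 1.96 × 0.283 = ± 0.55). An imbalance of one standard error moves the unadjusted DAP difference by r × 0.283, which is 0.06 SD at r = 0.2 and 0.17 SD at r = 0.6. The unadjusted test's own standard error, also 0.283 SD, already contains this variation. It is the precision loss of Step 2 seen from another side and does not raise the 5% error rate.

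**Step 4: systematic imbalance.** Suppose the two blocks truly differ by 0.5 SD in mean weight and Emboguide has no effect on DAP. The bias is 0.5r, the noncentrality is 0.5r/0.283, and the nominal 5% test rejects as follows:

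| r | Bias | False-positive rate |
|---|---|---|
| 0.2 | 0.10 SD | 6% |
| 0.3 | 0.15 SD | 8% |
| 0.4 | 0.20 SD | 11% |
| 0.5 | 0.25 SD | 14% |
| 0.6 | 0.30 SD | 18% |

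With a systematic shift of 0.2 SD the rate is 5.2% at r = 0.2 and 7.0% at r = 0.6.

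**The case against.** The case for leaving the plan alone has five parts.

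- **The size rests on an assumed correlation.** This stands. Two features of the protocol could keep r low: the weight ceiling narrows the covariate's range, and DAP also reflects difficulty from tortuosity, variant anatomy and atherosclerosis, which Sections 3 and 7 stress. The low end of the range must therefore be shown. A gain quoted only from r = 0.4 upwards (19% to 56%) would mislead.
- **Chance imbalance is not a bias.** This stands. A reader might infer that a chance difference in weight invalidates the unadjusted test. It does not, because its standard error already allows for that (Step 3).
- **No drift in weight is shown.** This also stands. A reader might infer that the DAP comparison is confounded by body size. The documents describe one centre, about 8 months of enrolment and the same eligibility criteria for both groups, and give no sign of a trend in weight. Sequential allocation leaves the possibility open, no more.
- **Weight is not simply available.** This stands in part. The exclusion needs only a check against a cutoff, and Section 17 limits collection to information from the procedure. The exact value would have to be added to the data collected.
- **Period and operator effects are the larger threat, and DAP is not primary.** Both are true. Adjusting for weight does nothing about the former, and a weight-adjusted ratio must not be presented as controlling for confounding in general. The latter lowers the priority in a feasibility study with no stated power target.

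None of this removes the case for collecting weight and using it. The gain ranges from slight to substantial, and the outlay is small.

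**Conclusion.** The point holds as a cheap improvement to the analysis of two non-primary endpoints. The facts about the plan are not in doubt: both DAP comparisons are unadjusted, the groups are sequential, and body size is not recorded although weight must be checked at screening.

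The size of the benefit is uncertain because it depends on r. Over 0.2 to 0.6 it runs from negligible (detectable difference 0.79 SD in place of 0.81 SD) to substantial (0.65 SD). Protection against systematic imbalance is a second benefit, but its value depends on a drift in weight that the documents do not show. The false-positive rates of 6% to 18% apply only if a 0.5 SD shift exists.

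The unadjusted test is a defensible choice and misses no stated target. The primary comparison of catheterization time is not directly affected. The calculations assume a linear relation between weight and log DAP with the same slope in both groups, and take a t-test on the log scale as the unadjusted reference. The plan itself does not commit to that scale.

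**What to change.** 1. **Section 7 and the case report form:** record actual weight at screening for every patient in both groups.
2. **Section 9, variable list:** add weight and tabulate it by group, so that any imbalance is visible.
3. **Section 9, analysis:** for total DAP and for fluoroscopy DAP, fit a linear regression of log DAP on group with weight as a covariate. Report the adjusted geometric mean ratio with its 95% confidence interval. Keep the planned t-test or Mann-Whitney test as a supporting result.
4. **Section 9, interpretation:** state that adjusting for weight addresses body size only and does not remove period or operator-learning effects from the Emboguide-first, control-second order.

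The cost is one form field, one degree of freedom, and a change of scale from a difference in means or medians to a geometric mean ratio. The Section 17 statement that only procedure information is collected also needs checking, and if necessary rewording, so that it covers weight. No procedure or visit changes.

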Subjects will have one or more medical imaging studies (x-ray like films) which use radiation (emission or transmission of energy in the form of waves or particles). The tests or treatments include a whole body CT scan. To give an idea about how much radiation **the patients** will get, we will make a comparison with an every-day situation. Everyone receives a small amount of radiation that cannot be avoided each year. Some of this radiation comes from space and some from naturally-occurring radioactive forms of water and minerals. This research gives your body the equivalent of about 3 extra years' worth of this natural radiation. Subjects will be exposed to radiation as per their standard of care treatment. The investigational group will be subject to additional radiation for the 3D

planning dataset, however this in turn might reduce the duration of prostate artery catheterization leading to similar or reduced radiation if the 3D dataset was not used.

12) **Potential Benefits to Subjects***

There are no current direct benefits for patients, however there may be advantages to future patients if it is determined that this technology can obviate the need for pre-procedure CT angiogram and increase the safety of the procedure by reducing the risk of non-target embolization.

13) **Sharing of Results with Subjects***

The results will not be shared with subjects as there is no direct advantage to the patient and they are not related to clinical outcomes of the procedure.

14) **Setting**

Patients will be identify and recruited at PAC Radiology Clinic. The study procedures will be performed at UMHC.

15) **Recruitment**

Patients who require PAE will be referred by their Urologist or will visit an Interventional radiologist. This is a single center study. The patients eligible for the PAE for BPH will be offered the study and informed consent will be obtained. Patients will be recruited for participation in the study during routine consultation for the prostate embolization procedure.

16) **Confidentiality**

Subject study files will be stored in a double locked cabinet to which only the investigators and research team have access. The address is [name]. The only member(s) of the study team with access to it will be [name]. The data will be stored for up to 2-3 years after the study is completed and will be destroyed in accordance with university policies thereafter.

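### Section 11 names a whole body CT scan that the design sections do not describe, and gives a research-radiation figure with no group and no source

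*Combined protocol and SAP*

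**What the plan says.** Section 11 (Risks to Subjects) opens with a general statement: "Subjects will have one or more medical imaging studies (x-ray like films) which use radiation". It continues "The tests or treatments include a whole body CT scan". After an explanation of natural background radiation it gives its only figure: "This research gives your body the equivalent of about 3 extra years' worth of this natural radiation". Two statements about who is exposed follow: "Subjects will be exposed to radiation as per their standard of care treatment", and then "The investigational group will be subject to additional radiation for the 3D" planning dataset. The section adds that shorter catheterization might offset this additional radiation.

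The design sections describe the imaging as follows.

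- Section 5 (Local Number of Subjects): "Currently cone-beam CT is performed routinely for all PAE cases". The first 25 patients have the 3D angiogram and Emboguide; the next 25 have neither.
- Section 7 (Study Design/Procedures Involved): "We will initially obtain a 3D rotational selective angiography of the internal iliac artery for study group". It also names conventional DSA, live fluoroscopy and contrast-enhanced cone-beam CT, the last as existing clinical practice at the center.
- Section 9 (Data Management) lists the dose variables: total dose area product (DAP), fluoroscopy DAP, and the planning-dataset dose for each side.

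A pre-procedure CT angiogram is mentioned in Sections 3 and 12, but only as something the technique might make unnecessary.

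**The concern.** Radiation is the only physical risk that Section 11 describes, so this paragraph carries the protocol's whole account of what participation may cost a patient. Two things in it do not match the rest of the document.

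First, it lists a test that no procedure section contains. A reader cannot tell whether patients are to have a whole body CT for the study, whether the phrase is a loose description of other imaging, or whether the sentence does not belong to this trial.

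Second, it attaches one exposure figure to the research as a whole, although the two groups differ in exactly the imaging that the research adds. A reader who wants to know what a study-group patient or a control receives because of the trial cannot find out. What is at stake is the accuracy of a stated safety figure, not the validity of an analysis.

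**Working it through.** There is little arithmetic to do. The check compares Section 11 with the sections that define the imaging.

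**Step 1: can the figure of about 3 years be reproduced?** No. That would need an effective dose for the research imaging (or a DAP with a conversion factor) and an annual background dose, with years = effective dose ÷ annual background dose. The documents give none of these, so the figure can be neither confirmed nor refuted.

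**Step 2: imaging by group.**

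| Imaging | Where described | Study group (25) | Controls (25) | Added by the research? |
|---|---|---|---|---|
| 3D rotational angiography, internal iliac artery | Sections 5, 7 | Yes | No | Yes |
| Cone-beam CT | Sections 5, 7 | Yes | Yes | No, already routine |
| DSA and fluoroscopy | Sections 2, 7 | Yes | Yes | Not described as added |
| Whole body CT | Section 11 only | Not stated | Not stated | Not stated |

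**Step 3: counts.** Procedures in Sections 5, 7 or 9 that include a whole body CT: 0. Patients with described research-added imaging: 25 of about 50, or 25/50 = half. Controls with described research-added imaging: 0 of 25.

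**Step 4: could another scan be meant?** The pre-procedure CT angiogram is the only conventional CT mentioned elsewhere. It is not presented as a study procedure or as whole body imaging, so it does not explain the sentence. Neither cone-beam CT nor selective internal iliac angiography is described as whole body.

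**Step 5: what does the figure cover?** The sentence refers to the research, which suggests an increment over usual care. On the imaging described, that increment comes from the planning dataset and so arises in the study group only. Section 11 does not say this. Nor does it say whether the figure includes the whole body CT, or whether it is before or after the offset that the section hopes for from shorter catheterization.

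**The case against.** The best defense is that Section 11 separates the groups shortly after the figure. Standard-of-care exposure for everyone plus an increment for the investigational group is a coherent account, and the figure can be read as that increment. On this view only one stray sentence and a missing group label remain. Much of this stands, and it rules out several stronger readings that a reader might infer.

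- *The statements in Section 11 cannot all be true.* The two exposure sentences are compatible: one gives a baseline, the other an addition.
- *Controls are told they receive 3 extra years.* No text assigns the figure to controls. What can be said is that it is not split by group.
- *The figure was calculated from the whole body CT.* The two sentences sit in the same paragraph, but no derivation is given. The figure could rest on the planning dataset alone.
- *The DAP comparison is incomplete or biased.* Both groups record total DAP, and Section 9 says that the study group's total includes the planning dataset. No exclusions are listed. A scan given to all subjects would occur in both groups. That a dose would be missed, or missed unequally, is conjecture.
- *The consent form is wrong.* It is not in the documents reviewed. The second-person wording in Section 11 hints at shared text, but that is inference.

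The defense does not remove the core. The later sentences distinguish the groups in words only: they give no separate figures and do not limit the stated one to the study group. They also leave the whole body CT unexplained. Carried-over template wording would account for the sentence but would not correct it.

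**Conclusion.** The point holds as a minor inconsistency in risk disclosure. Section 11 lists a radiation procedure that the design sections do not contain. It also gives an exposure figure with no group and no derivation, in a trial where the described research-added imaging falls on 25 of about 50 patients and on none of the 25 controls.

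The size of any error in the figure is unknown, because no dose is given. The catheterization-time endpoint, the sample size and the planned tests are unaffected.

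The conclusion rests on two assumptions: that Sections 5, 7 and 9 are meant to be a complete account of the study imaging, and that cone-beam CT is routine care, as Section 5 says. If a whole body CT is in fact intended, the inconsistency remains, but the omission then lies in the procedure sections rather than in Section 11. The documents do not show which is the case.

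**What to change.** Reconcile Section 11 with Sections 5 and 7:

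1. Either identify the whole body CT as a study procedure, stating in Sections 5 and 7 which group has it, or remove the sentence from Section 11. The sponsor must establish which reflects the intended conduct.
2. Restate the research-added exposure separately for the study group and the controls, based only on the reconciled procedures. Give the source of each figure: the acquisitions counted, the dose assumed for each and the background rate used. Say whether the figure is before or after any offset from shorter catheterization.
3. Check that any consent wording that uses the figure matches the corrected text.

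The cost is a wording amendment to the protocol, and to the consent form if it carries the figure. Correcting the wording adds no patients or procedures and changes no analysis.
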